### 5.1.3. Baseline

Each subject will undergo Baseline assessments outline in the Schedule of Visits and Assessments (Section 1.3). For subjects <18 years, if the Baseline (Day 0) visit occurs within 3 weeks of Screening, the Screening lab results may be utilized.

Randomization and IP kit assignment will take place, via IWRS, after the subject has been found to be fully eligible for participation. A subject will be considered enrolled into the study upon randomization.

### 5.1.4. Physical Examination

Physical examinations will be performed according to the Schedule of Visits and Assessments (Section 1.3). The physical exam will be limited to skin (including assessment of Fitzpatrick skin type at Screening only), lungs, and heart only.

Fitzpatrick skin phototype assessment will be rated as follows:

- I. Always burns easily; never tans (sensitive)
- II. Always burns easily; tans minimally (sensitive)
- III. Burns moderately; tans gradually (light brown) (normal)
- IV. Burns minimally; always tans well (moderate brown) (normal)
- V. Rarely burns; tans profusely (dark brown) (insensitive)
- VI. Never burns; deeply pigmented (insensitive)

### 5.1.5. Vital Signs, Height and Weight

Vital signs will be performed according to the Schedule of Visits and Assessments ([Section 1.3](#)).

Blood pressure, heart rate, and temperature will be measured while the subject is sitting/resting for at least 5 minutes.

Height will be collected at Baseline and Week 8.

Subjects should void prior to weight being taken and remove any objects of significant weight (i.e., jackets, outerwear, shoes, cell phones, wallet, key chains, etc.). A 5% unintentional weight loss from Baseline should be reported to the medical monitor.

### 5.1.6. Laboratory Tests

All tests listed in Table 2 will be performed according to the Schedule of Visits and Assessments ([Section 1.3](#)) unless otherwise noted. For subjects <18 years old, Screening safety lab results collected within 3 weeks of the Baseline visit may be utilized as the Baseline safety lab assessment. No food restrictions are required for the collection of specimens. In addition, laboratory safety tests may be performed at unscheduled time points, if deemed necessary by the Investigator. Laboratory samples will be sent to the central lab. Refer to the most current Central Laboratory Manual for collection, processing, shipping, and report receipt instructions.

**Table 2: Laboratory Tests**

Hematology	Serum Chemistry

• Hemoglobin

• Hematocrit

• Total and differential leukocyte count

• Red blood cell count with indices and morphology

• Platelet count

	

• Blood Urea Nitrogen

• Bilirubin (total and direct)

• Alkaline phosphatase

• Aspartate aminotransferase

• Alanine aminotransferase

• Albumin

• Sodium

• Potassium

• Chloride

• Glucose

• Creatinine

Urinalysis 

• pH

• Specific gravity

• Protein*

• Glucose

• Ketones

• Bilirubin

• Blood*

• Nitrite*

• Urobilinogen

• Leukocyte esterase*

	Additional Tests 

• Urine pregnancy test (for females of childbearing potential only)

• Serum pregnancy test (hCG) **

• FSH test (post-menopausal females only)

• Pharmacokinetic (PK) assessments

\*If urinalysis is positive for protein, blood, nitrite, and/or leukocyte esterase, a microscopic examination (for red blood cells, white blood cells, bacteria, casts, and epithelial cells) will be performed.

\*\*At Screening for FOCBP only

### **5.1.7. Patient Health Questionnaire Depression Scale (PHQ-8)**

The PHQ-8 Assessment (see [Appendix 2](#)) will be completed by adult subjects according to the Schedule of Visits and Assessments ([Section 1.3](#)).

PHQ-8 score is the sum of the responses for the 8 questions.

Five severity categories of depression are defined as follows:

- None – Minimal depression (0 to 4)
- Mild depression (5 to 9)
- Moderate depression (10 to 14)
- Moderately severe depression (15 to 19)
- Severe depression (20 to 24)

A subject with a PHQ-8 score of 10-14 should be referred to a mental health professional for evaluation, regardless of the reason for their change in score.

A subject with with a PHQ-8 score of  $\geq 15$  should be immediately referred to a mental healthcare professional and Investigators in consultation with the mental health professional should consider interruption or discontinuation of the IP.

### **5.1.8. Patient Health Questionnaire Depression Scale (Modified PHQ-A)**

The Modified PHQ-A Assessment ([Appendix 3](#)) will be completed by adolescent subjects (12-17 years old, inclusive) according to the Schedule of Visits and Assessments ([Section 1.3](#)).

Modified PHQ-A score is the sum of the responses for the 8 questions.

Five severity categories of depression are defined as follows:

- None - Minimal depression (0 to 4)
- Mild depression (5 to 9)
- Moderate depression (10 to 14)
- Moderately severe depression (15 to 19)
- Severe depression (20 to 24)

A subject with a modified PHQ-A score of 10-14 should be referred to a mental health professional for evaluation, regardless of the reason for their change in score.

A subject with a modified PHQ-A score  $\geq 15$  should be immediately referred to a mental health professional, and Investigators in consultation with the mental health professional should consider interruption or discontinuation of the IP.

### **5.1.9. Children's Depression Inventory 2 (Parent Report)**

The CDI-2 Assessment will be performed according to the Schedule of Assessments ([Section 1.3](#)) for subjects 9-11 years old, inclusive. Subjects 9-11 years old at the time of assent will complete the CDI-2 throughout the study.

The CDI-2 quantifies depressive symptomatology using reports from children/adolescents, teachers, and parents or caregivers. It is recommended for use in initial evaluation and is appropriate when there is a need for an assessment and robust description of a child's depressive symptoms.

This study will use the CDI Parent Report Form. An example of the Parent Report Form is presented in [Appendix 4](#).

A subject with a CDI-2 raw total score of  $\geq 21$  for females and  $\geq 22$  for males should be referred to a mental health professional for evaluation.

A subject with a CDI-2 raw total score of  $\geq 32$  should be referred to a mental health professional, and Investigators in consultation with the mental health professional should consider interruption or discontinuation of the investigational product.

### **5.1.10. Columbia-Suicide Severity Rating Scale (C-SSRS)**

C-SSRS Assessments will be performed according to the Schedule of Visits and Assessments ([Section 1.3](#)) for subjects 12 years old and older.

The administration schedule of the C-SSRS will be:

- The Baseline-Screening version ([Appendix 5](#)) will be used at Screening to provide a pre-treatment assessment baseline.
- On all subsequent visits, the Since Last Visit version ([Appendix 6](#)) will be used.
- A score greater than 0 at the Screening or Baseline visit in suicidal ideation may indicate the need for mental health intervention. The Investigator should not enroll the subject in the study.
- Any score greater than 0 in the suicidal ideation score may indicate the need for mental health intervention. The Investigator should give consideration for the subject to discontinue from the IP and prompt referral to a mental health professional and/or possibly the emergency room. The Medical Monitor should be contacted.

The C-SSRS administrator will be trained via C-SSRS training video. A training certificate for the administrator(s) will be on file in the trial master file at the site.

The Investigator must review the completed C-SSRS. A qualified mental health care provider must be available, immediately if needed, to refer the subject for further evaluation.

### 5.1.11. Local Tolerability Assessment

The Investigator Local Tolerability Assessment will be performed according to the Schedule of Visits and Assessments ([Section 1.3](#)).

Application site reactions will be graded at each timepoint. Irritation reactions are graded using the scale detailed in the following section ([Berger 1982](#)). **Reactions at the site of product application, which may occur post-Baseline, should be differentiated from the preexisting inflammation associated with the subject's seborrheic dermatitis.**

For the Baseline visit, when IP is applied in the clinic, the Investigator assessments will be conducted by the Investigator prior to IP application.

#### Dermal Response

- 0 = no evidence of irritation
- 1 = minimal erythema, barely perceptible
- 2 = definite erythema, readily visible; minimal edema or minimal papular response
- 3 = erythema and papules
- 4 = definite erythema
- 5 = erythema, edema and papules
- 6 = vesicular eruption
- 7 = strong reaction spreading beyond application site

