### 1.3. Schedule of Visits and Assessments

Study Procedure	Screen	Baseline Day 0	Week 2 Day 14	Week 4 Day 28	Week 8 a Day 56
Visit	1	2	3	4	5
Visit Window	-4 weeks		± 3 days	± 5 days	± 5 days
Informed consent/assent	X				
Medical/surgical history, demography	X				
Physical examination b	X	X			X
Fitzpatrick Skin Type	X				
I/E criteria	X	X			
Randomization		X			
Hematology, Chemistry, and Urinalysis c	X	X		X	X
Vital signs, weight, height d	X	X	X	X	X
IGA, Overall Assessment of Erythema, Overall Assessment of Scaling e	X	X	X	X	X
BSA f	X	X	X	X	X
DLQI/CDLQI g , Scalpdex	X	X	X	X	X
Daily WI-NRS h at home (non-clinic)			Day -7 through Day 56		
Local Tolerability Assessment i		X		X	X
Pigmentation Assessment j	X	X	X	X	X
C-SSRS, CDI-2/PHQ-8/PHQ-A k	X	X		X	X
Medical Photography l		X	X	X	X
Serum pregnancy test m	X				
Urine pregnancy test n		X		X	X
PK sampling o				X	X
IP application and subject/family training p		X	X		
Dispense investigational product kit q		X	X	X	
Dispense / review dosing diary		X	X	X	X
Weigh investigational product r		X	X	X	X
Compliance calculation s			X	X	X
Adverse event assessment t		X	X	X	X
Prior & Concomitant medications	X	X	X	X	X

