### **6.1.1. Determination of Sample Size**

A sample size of approximately 450 subjects is planned for the study.

The randomization scheme will be 2:1 (ARQ-154 foam 0.3% QD: matching vehicle QD). Randomization will be stratified by site and baseline disease severity (IGA = 3 or IGA = 4). Approximately 300 subjects will receive ARQ-154 foam 0.3% QD; approximately 150 subjects will receive vehicle foam QD.

A sample size of 450 subjects will provide at least 90% power to detect a 25% difference between treatment groups on IGA success at  $\alpha=0.01$  using a 2-sided Cochran-Mantel-Haenszel test stratified by the randomization factors. The results from a recent Phase 2a study (ARQ-154-203) of ARQ-154 compared to vehicle treatment were used to estimate treatment difference. Specifically, in the Phase 2a trial, 73.8% of subjects demonstrated IGA success in the ARQ-154 0.3% group and 40.9% of subjects demonstrated IGA success in the vehicle group.

The number of subjects to be enrolled will also provide sufficient power for the secondary endpoints. Additionally, the larger study size is included in order to provide additional/sufficient numbers of subjects on ARQ-154 treatment for a safety database.

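### Dermal Response score 4 in Protocol 5.1.11 is printed out of order: it repeats part of score 2 and names fewer signs than score 3

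*Protocol*

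**What the plan says.** Protocol 5.1.11 makes the printed list the working scale: "Irritation reactions are graded using the scale detailed in the following section". The section also cites a published source for that scale. Under Dermal Response, the four steps that matter here are:

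- "2 = definite erythema, readily visible; minimal edema or minimal papular response"
- "3 = erythema and papules"
- "4 = definite erythema"
- "5 = erythema, edema and papules"

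The Schedule of Visits (Protocol 1.3) places the assessment at Baseline, Week 4 and Week 8. At Baseline, "the Investigator assessments will be conducted by the Investigator prior to IP application".

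SAP 2.2.2 lists local tolerability among the safety endpoints. Protocol 6.2.4 and SAP 9.2 summarise the investigator's score both as counts and percentages per category and as mean and median. The planned outputs are Tables 14.3.2.1 (quantitative) and 14.3.2.2 (categorical). Protocol 5.9 uses the same scale to trigger a treatment interruption at a score of 5 or more. The SAP does not reprint the scale, and neither document defines score 4 anywhere else.

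**The concern.** An ordinal severity scale is useful only if each step is at least as bad as the one below it. A mean or median takes this for granted, and so does anyone who reads down a categorical table. At score 4 the printed scale does not meet that condition, because the descriptor goes back to a level of redness already reached at score 2 and drops the papules that define score 3.

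Two practical problems follow for a rater who grades by the printed words. Definite redness with nothing else matches score 4 exactly and also matches the opening of score 2, so the same skin can be graded 2 or 4. And a reaction with clear edema but no papules has no natural place on the scale. What is at stake is the reading of a descriptive safety summary, not the efficacy conclusion.

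**Working it through.** The plan states no figure on this point, so the check compares the descriptors sign by sign.

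| Score | Erythema | Edema | Papules |
|---|---|---|---|
| 1 | faint only | not named | not named |
| 2 | definite | at most minimal | at most minimal |
| 3 | named, no qualifier | not named | named, no qualifier |
| 4 | definite | not named | not named |
| 5 | named | named | named |

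Scores 6 and 7 move on to vesicles and to spread beyond the application site.

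**Steps in order.**
- 1 to 2: rises. Erythema goes from faint to definite, with minimal edema or papules added.
- 2 to 3: rises. Papules go from minimal and optional to a defining sign.
- 3 to 4: does not rise. Papules disappear and nothing is added. Signs named fall from 2 (erythema, papules) to 1 (erythema).
- 4 to 5: rises from 1 sign to 3 (erythema, edema, papules).

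Only the position of score 4 fails. With score 4 removed, the sequence 1, 2, 3, 5 is in order.

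**The gap.** Take a reaction with more than minimal edema and no papules. Score 2 caps edema at minimal. Score 3 requires papules and names no edema. Score 4 names no edema. Score 5 requires papules as well as edema. So nothing from 2 to 5 fits. A rater would have to choose a neighbouring score, and that choice could be 5 as well as something lower. The letter codes under Other Effects do not cover edema either.

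**Could another part of the documents settle score 4?** Protocol 5.9 restates score 5 only, with the same three signs as the list. No other text gives a descriptor for score 4.

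**Size.** The effect on a mean would need the frequency of the affected gradings in each arm, and the documents give none. The planned numbers ("Approximately 300 subjects will receive ARQ-154 foam 0.3% QD; approximately 150 subjects will receive vehicle foam QD") yield at most 450 x 3 = 1,350 investigator gradings, of which 450 x 2 = 900 come after the start of treatment. These count how often the scale is used, not how often score 4 misleads, so they are not a measure of the error.

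**The case against.** **The word for definite redness might mark a stronger erythema than at score 3.** This does not hold, because score 2 already reaches that level.

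**The protocol names and cites a published scale, so the printed list is only a transcription, and trained raters may have used the correct wording.** This stands in part. The eCRF and training materials are not in the documents, so a reader might infer that investigators graded by the faulty line, but nothing shows that they did. What the citation does not do is cure the printed text, since 5.1.11 directs grading by the list itself. The line also appears only once, so it is worth confirming against the signed protocol.

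**The consequences are small.** This stands. SAP 9 plans no inferential tests on safety. SAP 9.1 flags application-site adverse events separately in the listings. The interruption rule in Protocol 5.9 prints its own descriptor, consistent with the list. Protocol 2.3.1 reports good tolerability for the same foam and strength in phase 2a, including by investigator rating. That gives no score frequencies, but it suggests that the middle scores may be uncommon.

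**It is too late to matter.** This stands in part. SAP Section 1 records database lock on 17-May-2022 and unblinding on 19-May-2022, so no grade can be changed. Reporting can still be made clear, because SAP version 3.0 looks ahead to the Clinical Study Report and NDA.

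**Stronger readings to avoid.** A reader might infer that scores 2, 3 and 4 are all unreliably ordered. The step from 2 to 3 does rise, so only score 4 is out of place. A reader might also infer that score 4 was meant to name edema. The pattern of scores 3 and 5 points that way, but the documents do not contain the source scale and cannot confirm it.

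**Conclusion.** Wrong as written, and minor. This is a wording error in a scale that the protocol puts to use, not a design choice. As printed, score 4 repeats the start of score 2 and names less than score 3, and edema without papules has no distinct score between 2 and 5. The position of score 4 in Tables 14.3.2.1 and 14.3.2.2 therefore cannot be relied on, and the mean suffers more than the categorical counts because it treats 4 as worse than 3.

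The wording defect is certain on the printed text. Its effect on the tables is not: it depends on whether the eCRF and training carried this wording, and on how many gradings were affected, neither of which the documents show. Primary and secondary efficacy analyses, alpha and sample size are untouched. A reader might infer that the interruption rule is compromised. The documents do not support this, because the wording of its threshold is consistent in both places. The most that can be said is that a rater facing edema without papules would have had no fitting score below 5.

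**What to change.** 1. Correct the score 4 descriptor in Protocol 5.1.11 to match the source scale that the protocol cites. The sponsor needs that source to hand, because the right wording cannot be taken from the protocol or SAP.
2. Check whether the eCRF and the rater training carried the printed wording.
3. If they did not, leave the analysis and tables as planned.
4. If they did, footnote Tables 14.3.2.1 and 14.3.2.2 to say how score 4 was defined for raters, that it is out of order relative to scores 2 and 3, that edema without papules had no distinct score, and that the categorical table should be read in preference to the mean.

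Keep the prespecified mean, median and categorical summaries in either case. After database lock the correction reaches only the reporting of recorded grades and any later use of the scale. The cost is one descriptor line, one check and at most one footnote on two tables. No analysis is added or removed.

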#### Other Effects

- A = slight glazed appearance
- B = marked glazing
- C = glazing with peeling and cracking
- D = glazing with fissures
- E = film of dried serous exudates
- F = small petechial erosions and/or scabs
- G = no other effects

The Subject Local Tolerability Assessment will be performed according to the Schedule of Visits and Assessments ([Section 1.3](#)).

This assessment will be administered by the site 10 to 15 minutes after IP application in the clinic at Baseline and recall assessments at Weeks 4 and 8.

Grade	Sensation Following Investigational Product Application
0 (none)	No sensation
1 (mild)	Slight warm, tingling sensation; not really bothersome
2 (moderate)	Definite warm, tingling sensation that is somewhat bothersome
3 (severe)	Hot, tingling/stinging sensation that has caused definite discomfort

### **5.1.12. Pigmentation Assessment**

The Investigator will assess for pigmentation in areas affected previously and/or currently by seborrheic dermatitis according to the Schedule of Visits and Assessments ([Section 1.3](#)).

Hypopigmentation and hyperpigmentation will be scored individually using a 0 – 3 scale: ‘0’ for none, ‘1’ for mild, ‘2’ for moderate, and ‘3’ for severe.

### **5.1.13. Adverse Events**

Adverse events (AEs) will be collected and assessed throughout the study according to the Schedule of Visits and Assessments ([Section 1.3](#)). The Investigator is responsible for ensuring that all adverse events observed by the clinical staff or reported by the subject that occur after the first application of investigational product through the end of the study are recorded in the subject’s medical record and the eCRF.

The Investigator is responsible for ensuring that all serious adverse events observed by the clinical staff or reported by the subject that occur after signing of the informed consent through 30 days after the last day of the application of the investigational product or the end of study (whichever is later) are recorded in the subject’s medical record and are submitted per SAE reporting requirements ([Section 5.7.2](#)).

AEs (whether serious or non-serious) and clinically significant abnormal laboratory test value(s) will be evaluated by the PI and treated and/or followed up for up to 30 days after end of treatment or until the symptoms or value(s) return to the subject’s baseline value, or acceptable levels, as judged by the Investigator.

Refer to [Section 5.7](#) for further details on Adverse Events.

## **5.2. Efficacy Evaluations**

Investigators will be trained in the administration of rating scales. A training certificate is issued upon successful completion of the training and will be valid for 12 months, unless compliance issues are identified that warrant retraining.

### **5.2.1. Investigator Global Assessment (IGA)**

Investigator’s Global Assessments (‘whole body’ and ‘intertriginous area’) will be performed at according to the Schedule of Visits and Assessments ([Section 1.3](#)). The IGA should be completed prior to any other physician assessments.

The IGA is a static evaluation of qualitative overall seborrheic dermatitis severity. This global assessment scale is an ordinal scale with five severity grades (reported only in integers of 0 to 4). Each grade is defined by a distinct and clinically relevant morphologic description that minimizes inter-observer variability.

**Every effort must be made for the same Evaluator to complete the IGA for the subject at every study visit, particularly for Baseline and Week 8.**

### Investigator Global Assessment of Disease (IGA)

Score	Description
0	Clear: No erythema, no scaling (hypo-hyperpigmentation can be present)
1	Almost clear: Slight erythema and/or trace (barely perceptible) amounts of scaling
2	Mild: Pink to red color and/or slight scaling
3	Moderate: Distinct erythema (redness) and/or clearly visible scaling
4	Severe: Severe erythema (intense, fiery red) and/or severe scaling (coarse, thick scales with flaking onto clothes or skin)

#### 5.2.2. Overall Assessment of Erythema

Overall Assessment of Erythema will be performed according to the Schedule of Visits and Assessments ([Section 1.3](#)).

Overall Assessment of Erythema is a static qualitative evaluation, involving an ordinal scale with 4 severity grades (reported only in integers of 0 to 3). Each grade is defined by a distinct and clinically relevant morphologic description that minimizes inter-observer variability.

**Every effort must be made for the same Evaluator to complete the Overall Assessment of Erythema for the subject at every study visit, particularly for Baseline and Week 8.**

#### Overall Assessment of Erythema

Symptom	Score	Description
Erythema	0	None: No evidence of erythema
	1	Mild: Barely perceptible erythema which is faint or patchy
	2	Moderate: Distinct erythema,
	3	Severe: Intense (fiery red) erythema

